According to the Section 5 - Neuro-Ophthalmology in the *Basic and Clinical Science Course* textbooks, the workup for anisocoria, or unequal pupil size, is to be done according to a flow-sheet^{appx.1}. For anisocoria that is greater in bright light than dim light, a low-dose pilocarpine test is indicated to determine if the anisocoria is due to either Adie's tonic pupil or pharmacological dilation versus third cranial nerve palsy. If the pupil constricts to low-dose pilocarpine, the patient is determined to have Adie's tonic pupil, or parasympathetic denervation. However, if the pupil does not constrict with low-dose pilocarpine, a high-dose pilocarpine test is the next step in the work-up. If the pupil constricts to high-dose pilocarpine, the patient is determined to have a third cranial nerve palsy which then needs to be further evaluated with imaging including CT angiogram due to concern for aneurysm rupture. However, if the pupil does not constrict to high-dose pilocarpine, the patient likely has anisocoria due to pharmacological dilation. Suspected iatrogenic anisocoria does not require further evaluation with imaging as it should resolve as the pharmacological substance causing the dilation is metabolized. The flow chart in the *BCSC* books does not consider a phenomenon that may occur as the pharmacological substance causing dilation wears off. We propose that there is a period of time in which a pharmacologically dilated pupil may constrict to high-dose pilocarpine, but still appear dilated, and thus anisocoric. In this case, the patient would require additional imaging with CT angiogram, even though their history may not support any findings concerning for third nerve palsy due to aneurysm. Depending on the patient's history, conducting further imaging may have greater risks and financial burden that are unlikely to provide valuable information. If a patient has history of possible pharmacological dilation in absence of aneurysm symptoms including headache, nausea, vision changes, loss of consciousness, then the patient should not be further evaluated with imaging. We aim to demonstrate the period in which a pharmacologically dilated eye may appear anisocoric on exam, but still respond to 1% pilocarpine.

B. BACKGROUND AND SIGNIFICANCE

Proper workup of anisocoria that is greater in bright light is extremely important given the potentially dangerous causes of an inappropriately dilated pupil. Particularly, the reaction of the anatomically intact, inappropriately dilated pupil to 1% pilocarpine can be essential in distinguishing pharmacologic dilation from dilation caused by a third nerve palsy. Although third nerve palsies are often associated with ophthalmoplegia in addition to mydriasis, isolated mydriasis of the affected pupil can be seen in the early stages of compressive damage to the nerve.¹ Whereas pharmacologic dilation is a benign condition that involves no further workup, compressive third nerve palsy is a common presenting sign of conditions such as subarachnoid hemorrhage, intracranial mass, intracranial aneurysm, or cavernous sinus aneurysm.¹⁻³

If the current algorithm is followed, any anatomically intact, yet inappropriately dilated eye that contracts to 1% pilocarpine, but not to 0.1%, will be considered suspicious for a third nerve palsy. Our proposal to clarify the “wearing-off” period of pharmacologic dilation will provide those utilizing this algorithm with an alternative etiology for a pupil that constricts to 1% pilocarpine. This addition will help to avoid unnecessary and expensive workup for a suspected third cranial nerve palsy.

Currently, there is not any literature that describes the “wearing-off” period of pharmacological dilation as a cause of anisocoria in respect to acute clinical workup. Although there are examples of recent studies describing the potential use of constricting agents to reverse pharmacologically induced mydriasis, these studies have been limited in scope to symptomatic relief from the dilated eye and thus have not influenced the BCSC algorithm for the treatment of anisocoria in the acute setting.⁴ We believe that this study has the potential to save money and time, as well as reduce the stress that may be associated with consideration of a more serious diagnosis. These benefits will be applicable to the provider, as well as the patient, thus advancing patient-centered high-quality care.

C. PRELIMINARY STUDIES

There are no preliminary studies that are pertinent to this protocol.

[name], DO is a board-certified ophthalmic plastic & reconstructive surgeon. He will be overseeing the project’s academic and clinical aspects. He has completed CITI training through Prisma Health to conduct human subjects research.

[name] is a fourth-year medical student who is currently in good standing to graduate from the University of South Carolina School of Medicine Greenville in 2022. He has completed CITI training through the University of South Carolina to conduct human subjects research.

D. RESEARCH DESIGN AND METHODS AND DATA ANALYSIS

Recruitment of participants for this study will be done at the University of South Carolina School of Medicine Greenville. We will be recruiting 15 otherwise healthy participants with no significant ophthalmological history. Data collection will be done at the Prisma Health Eye Institute - Greenville. Data analysis will be performed by [name] at Prisma Health.

After participants are recruited, they will be brought into the ophthalmology clinic where they will first be consented for the study by a physician^{appx.5}. Following consent, participants will complete paperwork such as demographics^{appx.2}, contact information^{appx.3} and exclusion/inclusion criteria forms^{appx.4}. They will then be screened for hyperopia using a phoropter, have their intraocular pressures measured using a Reichert Tono-Pen Avia , and have their iridocorneal angle measured with a gono lens. The purpose of this exam is to screen out participants with hyperopia > +1 diopter, iridocorneal angles where trabecular meshwork cannot be seen for greater than half of the angle, and/or intraocular pressures of > 22 mm Hg, as these conditions may increase the risk for mydriatic agent-induced angle closure glaucoma^{appx.4}. An additional ophthalmic medication, proparacaine hydrochloride 0.5%, will be used to numb the eyes before measuring intraocular pressures and prior to gono lens examination. This medication is commonly used as an ocular surface analgesic during routine eye examinations. This screening exam will take place at least one day prior to administration of any dilating drops, as examination of the angle with gono lens may affect pupillary dilation through corneal contact. The initial exam will be performed by a physician licensed to practice ophthalmology.

After screening, participants will be asked to return to the clinic on a scheduled day (within a week of screening) to have their left eye dilated. At this visit, the diameter of their left pupil will be measured using a Near card in a windowless room with a set light-level. Tropicamide will be our agent of choice for pharmacological dilation. Tropicamide is widely used in ophthalmology clinics to dilate the pupil of the eye and has a suspected effect time of 4-8 hours of dilation.⁵ Participants will receive one drop of tropicamide in the left eye and, after the drops have had time to take effect, about 20-30 minutes, the diameter of the participant's pupil will be measured again. After measurement of baseline pupillary response to tropicamide, participants will be dismissed and asked to return to the clinic in 3-4 hours. At this time, we will record the diameter of the left pupil again and compare it to the participant's baseline as well as post-dilation diameter. One drop of 1% pilocarpine will then be administered to the participant's left eye. Pilocarpine 1% is a miotic agent that is the current standard for workup of anisocoria of unknown cause according to the 2021-2022 Basic and Clinical Science Course^{appx.1}. After the pilocarpine has been given 10-15 minutes to take effect,

any change in pupillary diameter will be measured. Following this measurement, participants will be dismissed. A positive result will be indicated by a constricting response of the pupil after administration of pilocarpine of > 1mm in diameter, while still appearing anisocoric on exam (clinically significant difference in pupillary diameter between right and left eyes). Application of dilating and constricting eye drops, as well as measurement of pupillary response will be performed by medical student volunteers. These volunteers will receive training on sterile eye-drop application technique as well as pupillary measurement using a Near card.

In the event that no response to 1% pilocarpine is observed at the initial post-dilation visit, or if pupillary diameter has returned to baseline prior to the administration of 1% pilocarpine at any point, we will ask this participant to return to the clinic on another day to have the process repeated in their right eye, with the modification of either shortening or lengthening the interval of reassessment based on their left eye's response to the drops. This is to avoid any confounding from the administration of subsequent pilocarpine eye drops in the same eye. If the left pupil returned to baseline pupillary diameter prior to the 3-4 hour reassessment, we will have them return 2-3 hours following dilation of their right eye to have their pupillary diameter checked and the administration of Pilocarpine 1% repeated. If the left pupil remained dilated with no response to 1% pilocarpine at 3-4 hours, we will have them return 4-5 hours following dilation of their right eye to have their pupillary diameter checked and the administration of Pilocarpine 1% repeated. Repeating the protocol with varied assessment times in the contralateral eye will be in an effort to compensate for expected variation in each participant's response to tropicamide and 1% pilocarpine. Despite this, it is possible that we will not be able to capture this critical window in each participant, if one exists. However, we do not believe it will be necessary to demonstrate the phenomenon in all participants, and a minimum of 2 positive results should be sufficient to demonstrate our proposed concept for this preliminary study.

E. PROTECTION OF HUMAN SUBJECTS

1. TARGET POPULATION:

We plan to conduct the study with 15 medical student volunteers at the University of South Carolina Greenville. Exclusion criteria include a history of angle closure glaucoma, any other type of glaucoma, or any elevated eye pressure readings as well as any history of intraocular surgery or procedure. Exclusion will also occur if the participant is found to be hyperopic to >+1 diopter, has an intraocular pressure of > 22 mm Hg in either eye, or displays an iridocorneal angle where trabecular meshwork cannot be seen for greater than half of the angle in either eye, as these features are known to increase the risk of angle closure glaucoma when using dilating eye drops.

Finally, those with a known allergy to natural rubber latex will be excluded from the study.

We chose a sample size of 15, as this is a proof of concept, and thus we would like to demonstrate a minimum of 2 instances of pharmacologically dilated eyes that constrict $> 1\text{mm}$ to 1% pilocarpine. We feel that at least 15 participants will be necessary to guarantee that we witness at least 2 instances of the proposed phenomenon, assuming that we test both of their eyes independently with varying timeframes of reassessment. If we limited the study to < 15 , we may not be able to witness the desired effect without subjecting participants to multiple rounds of testing.

If we are able to describe a period in which the pharmacologically dilated pupil responds to 1% pilocarpine with $>1\text{mm}$ of constriction but maintains the appearance of anisocoria that is worse in bright light in two or more participants, this study will serve as a pilot study to demonstrate the need for further research on the concept in order to make an addendum to the current treatment algorithm for anisocoria.

2. RECRUITMENT PLANS:

Recruitment of subjects will be done in person at the University of South Carolina School of Medicine Greenville, via the school newsletter that is sent to the student body on a weekly basis, and with email correspondence via the Ophthalmology interest group at the school. Approval has been obtained from school administration to conduct recruitment onsite and via electronic correspondence^{appx.6,7}.

3. EXISTING DATA/SAMPLES:

There are not any existing data or samples for this study.

4. CONSENT/ASSENT:

The participants will be asked to sign a consent form prior to participation^{appx.5}. The study doctor will consent the participants before any study procedures are completed. All communication will take place in a private setting. The participant will be given ample time to read the consent and have all questions answered prior to providing signature. The consent will be signed and dated by all parties and a copy will be provided to the participants at the time of consent. The consent will discuss risks of eye dilation including blurred vision for several hours following drop administration. Participants will also be informed of the risk of angle-closure glaucoma, and will be screened for any significant ophthalmological history, which will exclude them from the study. Participants will have ample opportunity to ask any questions concerning what to expect from and potential risks of dilating drops.

5. POTENTIAL RISKS:

Drug Tropicamide:

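### Do the left-eye and right-eye reassessment windows run on different clocks, so that a later retest could fall earlier?

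*Protocol*

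**What the plan says.** The timing rules stand in Section D (Research Design and Methods and Data Analysis).

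- **Left eye.** One drop of tropicamide is given. The pupil is measured "after the drops have had time to take effect, about 20-30 minutes". Then "participants will be dismissed and asked to return to the clinic in 3-4 hours". Taken literally, the 3-4 hours start at dismissal, after that reading.
- **Right eye, on another day.** The same procedure is repeated "with the modification of either shortening or lengthening the interval of reassessment". If the left pupil was already back to baseline, "we will have them return 2-3 hours following dilation of their right eye". The other branch reads "If the left pupil remained dilated with no response to 1% pilocarpine at 3-4 hours", and then "we will have them return 4-5 hours following dilation of their right eye". Whether dilation means the drop or the dilated state is not stated.

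Section E.1 (Target Population) bases the sample size of 15 on "assuming that we test both of their eyes independently with varying timeframes of reassessment". It describes success as follows: "If we are able to describe a period in which the pharmacologically dilated pupil responds to 1% pilocarpine" with more than 1 mm of constriction and persisting anisocoria, in two or more participants.

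**The concern.** The study asks about a period of time after dilation, so the origin of the clock is close to the subject of the study. The left-eye hours are worded from dismissal and the right-eye hours from dilation. If these are different moments, they differ by the 20-30 minutes of onset, which is a third to a half of an hour-wide window.

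Two consequences would be feared. First, a right-eye retest meant to come later than a failed left-eye test could come at about the same elapsed time, or earlier, which contradicts the stated purpose of the changed interval. Each participant has only one other eye, so that opportunity might be poorly used. Second, elapsed times from first and second eyes would not be on one scale when the period is described.

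**Working it through.** The protocol gives no figure to reproduce here; the check is interval arithmetic on its own windows.

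**Inputs (Section D).** Drop to reading: 20-30 min. Left-eye return: 3-4 h. Right-eye return: 2-3 h (shortened) or 4-5 h (lengthened). Dismissal is taken to coincide with the reading.

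**Step 1: windows on a clock that starts at the drop.** An interval counted from the reading is moved by 20 min at its lower end and 30 min at its upper end. For the left eye: 3h00 + 0h20 = 3h20 and 4h00 + 0h30 = 4h30. Overlap = smaller upper limit minus larger lower limit; a negative value is a gap.

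| Left eye from | Right eye from | Left window | Shortened window | Lengthened window |
|---|---|---|---|---|
| drop | drop | 3h00-4h00 | 2h00-3h00, touches | 4h00-5h00, touches |
| reading | reading | 3h20-4h30 | 2h20-3h30, overlap 10 min | 4h20-5h30, overlap 10 min |
| reading | drop | 3h20-4h30 | 2h00-3h00, gap 20 min | 4h00-5h00, overlap 30 min |
| drop | reading | 3h00-4h00 | 2h20-3h30, overlap 30 min | 4h20-5h30, gap 20 min |

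The 30-minute overlap arises only in the last two rows, where the origin changes between eyes. It can fall in either branch, depending on which eye has which origin. In the second row the windows only touch on their own clock; the 10 minutes come from variation in onset.

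**Step 2: how often a lengthened retest is not later.** Assume returns are uniform within each window and independent. Let U and V be uniform on (0, 1) h, and let g, the onset time, be uniform on (1/3, 1/2) h.

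- *Third row.* Shift D = (4 + V) - (3 + U + g) = 1 + V - U - g. The mean is 1 - 5/12 = 7/12 h = 35 min; the range is -30 to +100 min. Given g, P(D ≤ 0) = g²/2. E(g²) = (1/8 - 1/27)/(3 × 1/6) = 0.1759, so P(D ≤ 0) = 0.088. P(D < 0.5 h) = E[(0.5 + g)²]/2 = 0.8426/2 = 0.421.
- *First row.* D = 1 + V - U. The mean is 60 min, P(D ≤ 0) = 0 and P(D < 0.5 h) = 0.5²/2 = 0.125.
- *Second row.* D = 1 + V - U + g₂ - g₁. The minimum is -10 min. P(D ≤ 0) = E[(g₁ - g₂)²]/4 = (1/216)/4 = 0.0012.

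**Step 3: sensitivity and expected counts, third row.** If returns cluster mid-window (triangular), P(D ≤ 0) = 0.022. If left-eye returns run late (Beta(2,1)) and right-eye returns early (Beta(1,2)), it is 0.257. The number of lengthened retests is not given. At 0.088, five such retests give 5 × 0.088 = 0.4 expected reversals, and all 15 participants give 15 × 0.088 = 1.3.

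**Step 4: which row the text supports.** Section D repeats the procedure in the other eye and names only the interval as changed, so the origin carries over. It also sets 2-3, 3-4 and 4-5 hours side by side, which form adjoining windows on one scale. Both features point to the first or second row. No sentence announces a change of origin.

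**Step 5: what the outcome uses.** A positive is constriction of more than 1 mm after pilocarpine with persisting anisocoria. Success is at least two positives. Neither contains an elapsed time.

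**The case for a change.** The strongest case for a change is that elapsed time is what the study wants to describe, that visit timing belongs in the protocol rather than in an analysis plan, and that the literal text does place the left-eye origin at dismissal. Student volunteers give the drops and take the readings, so a written rule should not need interpretation. On mixed origins the mean shift of a lengthened retest falls from 60 to 35 minutes, and 42% of such retests come less than 30 minutes later, against 12.5% on a common drop clock. Naming one origin would cost almost nothing.

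The arithmetic and the absence of a named time zero stand. The step from there to harm does not. The documents give no curve of pilocarpine response against time, so a smaller shift cannot be turned into fewer positives. Comparing the third row with the first, the lengthened retest falls at the same 4-5 h after the drop in both; only the left-eye test moves, and whether that finds more or fewer positives is unknown. A retest at a similar time is still a further test, in another eye on another day. The protocol describes no pooling by hour label, and the appendix forms, which are not shown, may already record times.

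**Conclusion.** The concern is right that no common origin is named, but it does not call for a change. On the reading that Section D best supports, one clock for both eyes, a lengthened retest precedes the left-eye test in 0% of cases (both from the drop) or 0.1%, by at most 10 minutes (both from dismissal). Only if the origin changes between eyes does a 30-minute overlap arise. The reversed share is then 8.8% under uniform, independent returns, and 2% to 26% under the other return patterns tried.

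Even then, the criterion of at least two positives is unaffected, no false positives are created, and no loss of yield can be shown from the documents. Section D already accepts that the window may be missed in some participants. In a 15-person proof of concept with hour-wide windows and an approximate onset time, this is a gap that staff and analysts fill by using one origin and reporting positives by recorded elapsed time. If the text is revised for other reasons, the left-eye and right-eye wording can be reconciled to one origin of the sponsor's choosing. The conclusion rests on the common-clock reading and on the success rule containing no timing condition.

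### Does the pilot need averaged triplicate pupil readings before a constriction of more than 1 mm can be trusted?

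*Protocol*

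**What the plan says.** The measurement plan is in Protocol Section D. At the return visit, 3 to 4 hours after tropicamide, the pupil is measured before pilocarpine: "At this time, we will record the diameter of the left pupil again". It is measured again 10 to 15 minutes after the drop, and then "Following this measurement, participants will be dismissed". The definition of a positive has two parts. The first is "A positive result will be indicated by a constricting response of the pupil after administration of pilocarpine of > 1mm in diameter". The second is "while still appearing anisocoric on exam (clinically significant difference in pupillary diameter between right and left eyes".

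Readings are made with a Near card under controlled lighting by student volunteers, and "These volunteers will receive training on sterile eye-drop application technique as well as pupillary measurement using a Near card". No sentence gives the number of readings per timepoint, and none mentions averaging.

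A right-eye retest is offered "In the event that no response to 1% pilocarpine is observed at the initial post-dilation visit", or if the pupil was already back at baseline. The success rule is that "a minimum of 2 positive results should be sufficient to demonstrate our proposed concept for this preliminary study". Section E.1 limits what success means: "this study will serve as a pilot study to demonstrate the need for further research on the concept".

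**The concern.** The success rule is short and depends on few calls. Two threshold crossings among 15 participants settle it, and each crossing is a dichotomised difference between two card readings. If each reading is single and noisy, chance can push an unresponsive eye past 1 mm or hide a real response. The right-eye retest gives some non-responders a second chance to cross. The protocol states no reading error and makes no quantified allowance for it. It is natural to ask whether two positives could be measurement noise, and whether averaging three readings by the same volunteer at each timepoint would be a cheap cure. If so, the pilot could report a phenomenon that it had not seen.

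**Working it through.** **Inputs from the protocol.** Cut: a fall of more than 1 mm (Section D). Success: at least 2 positives (Section D). Participants: 15 (Section E.1). The protocol gives no error rate or power to reproduce.

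**Assumptions, none of them in the protocol.** Single-reading SD s of 0.3 to 0.5 mm; pre-post error correlation r of 0 to 0.5; card step continuous, 0.5 mm or 1 mm; replicate correlation ρ of 0 to 0.8; no true response in any eye; independent eyes; anisocoria condition always met.

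**Step 1. False crossing from one pair of readings (continuous).**

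q = 1 − Φ(1 / (s·√(2(1 − r))))

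P(at least 2 of 15) = 1 − (1 − q)^15 − 15·q·(1 − q)^14

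Example: s = 0.5 and r = 0 give 1/(0.5 × 1.414) = 1.414, so q = 0.0786 and P = 0.333.

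| s (mm) | r = 0 | r = 0.3 | r = 0.5 |
|---|---|---|---|
| 0.3 | 0.8% | <0.1% | <0.1% |
| 0.4 | 11% | 2.7% | 0.4% |
| 0.5 | 33% | 15% | 4.5% |

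**Step 2. Adding the retest.** If every eye showing no constriction is retested, half of the unresponsive eyes get a second test (continuous readings), so q becomes 1.5q. At s = 0.5 the figures rise from 33% to 54% (r = 0) and from 4.5% to 9% (r = 0.5). At s = 0.3 and r = 0 the figure is 1.8%. So at SD 0.3 mm every figure stays below 2%, and only an SD of about 0.4 to 0.5 mm makes the point matter.

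**Step 3. Rounding to a card step.** A card read in steps cannot show a fall just over 1 mm. The smallest recordable fall above 1 mm is 1.5 mm on a 0.5 mm card and 2 mm on a whole-millimetre card. At s = 0.5 and r = 0, this cuts the chance of false success in first tests from 33% to 13% (0.5 mm steps) and 5% (1 mm steps).

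**Step 4. The mean of three readings.** For continuous readings s is replaced by s·√((1 + 2ρ)/3). The stepped cases with correlated replicates were simulated with 2,000,000 eyes each. Chance of at least 2 false positives in 15 first tests, s = 0.5, r = 0:

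| Card | one reading | three, ρ = 0 | three, ρ = 0.5 | three, ρ = 0.8 |
|---|---|---|---|---|
| continuous | 33% | 0.5% | 13% | 25% |
| 0.5 mm steps | 13% | 0.3% | 8% | 18% |
| 1 mm steps | 5% | 0.3% | 7% | 11% |

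Averaging lets the mean difference take values between card steps, so it removes the safeguard in Step 3. When replicates are highly correlated it removes little noise in return, and false success goes up.

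**Step 5. Detection of a true 1.5 mm fall** (s = 0.5):

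| Card | one reading | three, ρ = 0 | three, ρ = 0.5 | three, ρ = 0.8 |
|---|---|---|---|---|
| continuous | 76% | 89% | 81% | 78% |
| 0.5 mm steps | 64% | 84% | 76% | 73% |
| 1 mm steps | 50% | 76% | 70% | 65% |

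Detection improves in every case, by 2 to 26 percentage points.

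**The case for a change.** The best case for the concern is that a single pair is the natural reading of Section D, that two calls carry the whole conclusion, and that two further readings per timepoint cost minutes and need no new staff or equipment. Detection improves under every assumption tried, and this serves the protocol's own worry about missing the critical window. Replicates would also supply the repeatability estimate that the documents lack.

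Much of this stands. Averaging would be a reasonable choice, and the detection gain is real. What does not stand is the step from there to a defect. The number of readings is unstated, and such detail can sit in the volunteers' training or on a data form. The alarming figures of 33% and 54% come from the least favourable assumptions: the largest SD considered, independent continuous errors, no true response in any eye, and every eye still counting as anisocoric. Training, fixed lighting, the 1 mm margin and the need for two instances all work against that combination. Successive readings by one volunteer, with no masking described, could well be strongly correlated, which is where averaging stepped readings makes false success more likely. Expectation bias would remain as well. The undefined size of a clinically significant anisocoria is a separate question that averaging the treated pupil would not touch.

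**Conclusion.** The concern does not hold. The protocol states nothing wrong on this point and does not contradict itself, and it does not commit the study to single readings. The chance of false success lies anywhere from under 1% to 33% in first tests, and up to 54% with the retest, depending wholly on assumed SDs of 0.3 to 0.5 mm, card steps and correlations. The suggested remedy is a trade-off. It helps detection throughout, but at SD 0.5 mm and replicate correlation 0.8 it raises false success from 13% to 18% (0.5 mm steps) or from 5% to 11% (1 mm steps). The consequence of a false success is also small, because Section E.1 claims no more than a case for further research. Whether to take repeat readings is the investigators' preference, and the plan needs no correction here.

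### The positive rule does not use the post-dilation diameter already recorded, so eyes with no measured recovery count towards a concept described as wearing off

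*Protocol*

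**What the plan says.** The protocol's opening section proposes that, as a dilating drug wears off, there is an interval in which the pupil still looks dilated yet constricts to high-dose pilocarpine. Section B carries this into the intended use: "Our proposal to clarify the “wearing-off” period of pharmacologic dilation will provide those utilizing this algorithm with an alternative etiology".

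Section D plans four diameters per tested eye:

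- a baseline before tropicamide;
- a post-dilation reading: "about 20-30 minutes, the diameter of the participant's pupil will be measured again";
- a revisit reading after the participant is "asked to return to the clinic in 3-4 hours", where the investigators "we will record the diameter of the left pupil again and compare it to the participant's baseline as well as post-dilation diameter";
- a reading 10-15 minutes after one drop of 1% pilocarpine.

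The scoring rule that follows has two parts. The first sets the size of the response: "A positive result will be indicated by a constricting response of the pupil after administration of pilocarpine of > 1mm in diameter". The second concerns the comparison with the fellow eye, and the response counts only if it occurs "while still appearing anisocoric on exam (clinically significant difference in pupillary diameter between right and left eyes".

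Section D also says that two positive results are enough to demonstrate the concept. Section E.1 restates the criterion for two or more participants as more than 1 mm of constriction with anisocoria that is worse in bright light. On duration, section D says that tropicamide "has a suspected effect time of 4-8 hours of dilation".

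**The concern.** The explanation offered is that responsiveness returns during recovery. The scoring rule does not ask whether any recovery has taken place. The comparison of revisit with post-dilation diameter is planned, but no threshold, classification or conclusion depends on it.

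Two situations therefore give the same positive:

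- a partly recovered pupil responds, as the wearing-off account expects;
- a pupil with no measured recovery responds, which suggests that 1% pilocarpine can overcome tropicamide without recovery.

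The second raises a question about the pilocarpine test itself. It does not mark out a period within which the test misleads. An addendum to the anisocoria algorithm, the longer-term goal in section E.1, would read differently in the two cases.

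**Working it through.** **The plan's own figure.** Section E.1 gives 15 participants as the number needed to see at least two instances. It states no response rate, so 15 cannot be reproduced. For orientation, with X positives among 15 independent participants at rate p, P(X ≥ 2) = 1 − (1−p)^15 − 15p(1−p)^14. This gives 0.171, 0.451, 0.833 and 0.965 for assumed rates of 5, 10, 20 and 30%. The present point concerns what is counted, not the sample size.

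**The rule applied literally.** All diameters are illustrative; the protocol gives none. Baseline and fellow eye are 4 mm. The protocol sets no threshold for clinically significant anisocoria, so 1 mm is assumed, and 1 mm is also assumed for measurable recovery. Percent recovery = 100 × (post-dilation − pre-pilocarpine) / (post-dilation − baseline).

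| | Eye A | Eye B |
|---|---|---|
| Post-dilation | 8 mm | 8 mm |
| Revisit, before pilocarpine | 8 mm | 6.5 mm |
| After pilocarpine | 6.5 mm | 5.2 mm |
| Constriction | 8 − 6.5 = 1.5 mm | 6.5 − 5.2 = 1.3 mm |
| Residual anisocoria | 6.5 − 4 = 2.5 mm | 5.2 − 4 = 1.2 mm |
| Percent recovery | (8 − 8)/(8 − 4) = 0% | (8 − 6.5)/(8 − 4) = 37.5% |
| Positive as written | yes | yes |
| Partly recovered | no | yes |

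Both eyes are positive, but only eye B shows any wearing off.

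**Whether eye A is plausible.** The revisit is 3-4 hours after dismissal, and dismissal follows the 20-30 minute reading. Counted from the drop, that is about 3 h 20 min to 4 h 30 min, against a stated effect of 4-8 hours. The test thus falls around the lower end of the protocol's own range, where some eyes may have recovered little.

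**Whether another rule catches it.** Section D triggers a repeat in the right eye in two cases: the pupil is back at baseline, or it does not respond. An eye that is still dilated and does respond triggers nothing and is counted.

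**Possible size.** Assume that 30% of 15 participants are positive as written and that a share of those are unrecovered. For p = 0.30, P(X ≥ 2) = 1 − 0.0047 − 0.0305 = 0.965.

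| Unrecovered share of positives (assumed) | Recovered rate | P(≥ 2 recovered) | Unrecovered rate | P(≥ 2 unrecovered) |
|---|---|---|---|---|
| 0% | 30% | 0.965 | 0% | 0 |
| 25% | 22.5% | 0.883 | 7.5% | 0.312 |
| 50% | 15% | 0.681 | 15% | 0.681 |
| 75% | 7.5% | 0.312 | 22.5% | 0.883 |
| 100% | 0% | 0 | 30% | 0.965 |

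The chance of meeting the written criterion is 0.965 in every row. What two positives can be said to show changes from row to row.

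**The case against.** The strongest reply is that the rule matches the stated aim. The opening section sets out to show when a dilated, anisocoric eye can still respond to 1% pilocarpine, and the success statement in section E.1 speaks of the pharmacologically dilated pupil without mentioning wearing off. This stands: the narrower aim can be met without recovery, so the definition of a positive need not change.

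A reader might go further and infer that the trial cannot attribute a response to wearing off at all. The documents do not support that. All the diameters are recorded and the comparison is planned, so positives can be split by recovery afterwards. The gap lies in the rules, not in the data. The right-eye repeat also gives some evidence on timing: no response at 3-4 hours in one eye and a response at 4-5 hours in the other would suggest time dependence. That evidence is limited, because it arises only in early non-responders and compares different eyes on different days.

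A reader might also infer that requiring partial recovery would establish wearing off. It would not. Pilocarpine is not given at the 20-30 minute reading, so a half-recovered responder might also have responded when fully dilated. That reading may not be the maximum either, so recovery can be misjudged.

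Finally, section E.1 commits only to calling for more research, and either mechanism would justify that. This limits the consequence. It does not remove it, because sections A to B name one mechanism as the explanation and the planned readings can separate the positives that fit it from those that do not. A derived variable could be left to an analysis plan, but the protocol itself fixes the positive rule and the two-participant criterion.

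**Conclusion.** The point holds in a limited form. As written, an eye with no measured recovery can be counted towards a concept that the protocol describes as wearing off, and two such eyes would meet the criterion. They would support the statement that dilated eyes can respond to 1% pilocarpine, but not a wearing-off period.

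That an unrecovered eye can count follows from the text alone. How often it would happen is unknown. The fall from 0.965 to 0.681 rests on an assumed 30% positive rate, half of it unrecovered, with 15 independent participants each counted once; other shares give anything from 0.965 down to 0. This is an inexpensive improvement to what may be concluded, not a flaw that invalidates the study.

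**What to change.** Keep the definition of a positive response and add the following to section D and section E.1.

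1. For each tested eye, compute percent recovery by the formula above.
2. State a measurement tolerance for the pupil gauge, since the protocol gives none.
3. Report positives in two groups: partly recovered (pre-pilocarpine diameter below post-dilation and above baseline, each by more than the tolerance) and no measurable recovery.
4. Attribute the result to wearing off only if at least two participants fall in the first group. Otherwise conclude only that dilated eyes can respond to 1% pilocarpine.
5. State two limits: the 20-30 minute reading may not be the maximum, and partial recovery is consistent with wearing off but does not prove it, because pilocarpine is not given at that reading.

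The cost is some wording, one derived variable and one tolerance, with no added visit, drop or measurement. The drawback is that some positives will move to the second group, so the count that supports wearing off may be smaller. Fixing the split in advance avoids choosing it after seeing the results in 15 people.
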